## **Methods and Measures**

### **Design**

The proposed study will be the first to employ a randomized, double-blind, placebo-controlled design to parametrically evaluate the longitudinal effects of 16 days of rTMS to the DPFC (Aim 1) or the MC (Aim 2) on self-reported pain and the brain’s response to pain. This will be done in

a cohort of patients recruited from WFU clinics and the outer community with chronic lower back pain. Participants will be randomized to receive TMS to the DPFC, MC, or sham (50% at each site), using a Latin square randomization. Resting state connectivity will be collected at each MRI scanning session. Quantitative Pain Testing will be collected 11 times. MRI data will be collected 3 times: before the 1st visit of TMS, before the 12th visit of TMS, and before the 16th visit of TMS.

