### **Sample Size**

A power estimate for Aim 1 and 2 was prepared using an original fMRI dataset previously collected in our laboratory (8). In this experiment, 18 healthy controls performed the same fMRI pain paradigm as the present study before and after a single session of 10 Hz rTMS. Mean parameter estimates for the “heat pain vs. rest” condition were extracted from several *a priori* regions of interest. These data yielded an effect size which ranged from 0.70 (thalamus) to 1.08 (insula) (n=15 yields 80% power using a two-sided p<0.05). Allowing for a 10% dropout rate after the screening visit, and up to a 20% dropout rate at the end of the Treatment phase (Week 4), as well as a 10% data loss rate for MRI (Aim 2) due to individuals with excessive head motion in the MRI scanner, screening 58 individuals should lead to complete data from 48 individuals (16 real DPFC, 16 real MC, 16 sham (50% at each site)). Randomization will be handled by a Latin Square design with replacement will be used to ensure even enrollment across groups with replacement. All individuals will be enrolled at WFUHS. Data analysis and quality assessment will be ongoing.

Due to several COVID related factors, including challenges with scheduling and hesitation that participants may have wearing a mask in the MRI scanner, some participants will not receive the MRI

portion of this experiment. This will not affect our total enrollment goals, nor compromise the scientific integrity of this study. Moreover, it will lower the risk associated with MRIs to these participants.

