**Strategy 2: iTBS to the MC.** This protocol is identical to that used for the DPFc explained above, with the exception of using 90% RMT rather than 110% RMT.

During each real and sham TBS session each day the amplifier output will be escalated (“ramping” in 5% increments over 30 seconds) to enhance tolerability. The time between the end of the TBS procedures and the beginning of the behavioral assessments will be compiled and used as covariates in subsequent analyses.

**TMS ACTIVE SHAM system:** The MagVenture MagPro system has an integrated, active sham which passes current through two surface electrodes placed on the scalp. The electrodes will be placed on the left frontalis muscle for all sessions. A patient ID card will randomize participants to receive either real or sham stimulation. This system maintains blinding by a gyroscope in the coil which indicates to the clinical staff whether the coil should be rotated up or down for this participant once the card is entered into the machine. One side of the coil is active, the other is sham. To assess the integrity of the blind (active sham) a questionnaire will be given to both the patients and to the research staff at day 1, 6, 10 to evaluate their opinion on whether they received real or sham, their level of confidence (Likert scale 1-10), and their rationale (text entry).

**Assessments:** The primary dependent measures will be extracted from the Quantitative Sensory Testing for pain thresholds. Other assessments include: Brief Pain Inventory (BPI), the pain craving form, and subjective pain rating scales, delivered before and after TMS. Participants will also complete the Beck Depression Inventory (BDI-II), the Profile of Mood States (POMS), the Pittsburgh Sleep Quality Index (PSQI), the State-Trait Anxiety Inventory (STAI), and Barratt Impulsiveness Scale (BIS), which assesses anxiety and depression measures. Though these are not primary outcomes, the results will be used in post-hoc analyses of the data. All surveys will be filled out by the patient on tablet computers (Apple iPad/Microsoft Surface) and data entry will be done directly via Redcap Software.

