### **Outcome Measure(s)**

- A. Quantitative Sensory Testing.** The QST pain assessment produces 3 output variables: sensory threshold, pain threshold, tolerance threshold (all expressed in kiloPascals). The hypothesis will be tested using a within-subject repeated measures design (time x treatment) wherein time is the repeated variable and Real or Placebo TMS is the grouping variable. Given that the purpose of this pilot study is to develop effect sizes for a subsequent R01, we will derive least-squares means effect sizes of this strategy on these thresholds. Secondary analyses will evaluate the relationship between QST levels and the neural response to pain, as well as the relationship between QST values and evoked cortical responses. Integrating these measures together will provide a more complete picture of how cortical activity is able to modulate the pain response.
- B. Questionnaires and Evaluations.** The Opiate Pain inventory produces 4 output variables of interest: level of discomfort, level of pain, urge to use opiates, amount willing to pay for an opiate. The hypotheses for the Aims will be tested using a within-subject repeated measures design (time x treatment) wherein time is the repeated variable and Real or Placebo TMS is the grouping variable. Given that the purpose of this pilot study is to develop effect sizes for a subsequent R01, we will derive least-squares means effect sizes of our research strategy on these 4 variables, to determine the unique contributions of this intervention.

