**Expected (and alternative) Outcomes:**

- A. **Quantitative Pain Testing.** Based on our pilot data, we expect an interaction between treatment (Real DPFC or MC TMS vs. Sham) and time (Before vs. After rTMS) on the painfulness QST measure but no effect on sensory or tolerance levels. Alternative outcomes: It is possible that individuals will experience a small level of acute pain relief from their normal regimen of medication. We will be collecting information on opiate dose and timing at each visit to be used as potential covariates. Further, there is the possibility that pain tolerance will rise, possibly also reflecting improvements in executive function.
- B. **Qualitative Pain Assessment.** We expect reductions in pain and discomfort when comparing active vs sham. However, based on prior data in opiate dependent individuals, we expect the effect size of DPFC rTMS in to improve measures of Control but not measures of mood, whereas MC will have a larger effect on mood.
- C. **Neuroimaging.** At baseline we expect that there will be elevated activations in the Pain Network in individuals with chronic pain. Following sham stimulation, we do not anticipate a significant reduction of this response. Based on prior studies by our group in non-opiate dependent individuals, following LTP-like stimulation of the DPFC, we expect a significant amplification of the DPFC (% BOLD signal change), and a reduction of the Pain Network (dACC, anterior insula) reflecting the increased influence of executive processes.

Alternative outcomes: Though pilot data suggest that a single treatment will acutely reduce self-reported pain, it is possible that the neural circuits in opiate dependent individuals do not have the same ‘plasticity potential’ as in controls. If we fail to replicate prior work showing DPFC activation, this could reflect executive deficits (58), suggesting that the MC TMS will be more efficacious.

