**Exploratory Analysis:** We will evaluate if there are rate-dependent effects between baseline SN connectivity with the ECN and DMN and the efficacy of each TMS strategy on subjective pain. Data will be analyzed by using multivariate pattern analysis (MVPA) (2014). While the primary outcomes will be MRI V1 vs V2, we will also examine the relative ‘durability’ of the effects on pain by comparing the MRI data at the 1 month follow up between and within groups with factor analysis. **Integration of Brain based and Behavioral Based Outcomes with Gender and other Demographic Variables:** Finally, we will compare the relative efficacy of these two types of TMS using the behavioral and neuroimaging measures. Specifically, we will determine the effect sizes for DPFC and MC (relative to sham) stimulation on reducing the 1) the neural and 2) behavioral responses to pain, as well as 3) changes in clinical assessment metrics (see Approach). We will investigate the role of baseline cortical responsiveness on the pain response, as well as how changes in that evoked response are related to changes in both pain and craving measures. This will be specifically addressed as a factor of gender as

well, given that there are established differences in sensitivity to pain and prevalence of opiate dependence between men and women.

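### Per-site effects use one mixed-site sham group, so any difference in placebo response between the DPFC and MC sites enters them by half and the site comparison in full

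*Combined protocol and SAP*

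**What the plan says.** All references are to the combined protocol and SAP.

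- **Allocation.** Design: "Participants will be randomized to receive TMS to the DPFC, MC, or sham (50% at each site), using a Latin square randomization". Sample Size gives the numbers: "16 real DPFC, 16 real MC, 16 sham (50% at each site". This makes four cells: real DPFC 16, real MC 16, DPFC sham 8, MC sham 8.
- **Models.** Under Outcome Measure(s), the QST and questionnaire analyses are time-by-treatment designs in which "time is the repeated variable and Real or Placebo TMS is the grouping variable".
- **Per-site effects.** Expected (and alternative) Outcomes anticipates an interaction of time with "treatment (Real DPFC or MC TMS vs. Sham". The exploratory paragraph that follows says "we will determine the effect sizes for DPFC and MC (relative to sham) stimulation" and compares the efficacy of the two strategies. The Objectives say that this relative efficacy will inform a larger trial.
- **Covariates.** Those named are sessions received, time from stimulation to assessment, sex, depression score, duration of opiate use, time since last dose, and opiate dose and timing. Sham site is not among them. The Analytical Plan adds only general tests.
- **Procedure by site.** General Methods describes the MC protocol as the DPFC one "with the exception of using 90% RMT rather than 110% RMT". The marked cap is for dPFC placement only. For the sham system, "The electrodes will be placed on the left frontalis muscle for all sessions".

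**The concern.** Aim 1 evaluates DPFC stimulation and Aim 2 evaluates MC stimulation. Each needs a control that had the same procedure apart from the active field. As written, half of the control for each Aim had the other site's procedure: a different coil position and, for DPFC only, the cap. The stimulation setting may differ too, but that sham output follows its site's setting is an inference. If these features change expectation or placebo response, one site's effect is flattered and the other's reduced by the same amount, and the comparison of the sites carries the whole difference. The pilot's stated purpose is to supply effect sizes for a later trial, so a shift in the estimates matters at least as much as a shift in p-values. Randomising sham at both sites makes a matched comparison possible, but no stated analysis uses it.

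**Working it through.** **Inputs.** Cell sizes 16, 16, 8 and 8, and effect sizes 0.70 to 1.08 (Sample Size). The placebo difference D, DPFC minus MC, is not in the documents. It is assumed at 0.2 to 0.8 SD of the analysed outcome.

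**The plan's own figure.** Sample Size says n=15 gives 80% power at two-sided 0.05. Read as a two-sample t-test with 15 per group, power is 81.5% at 1.08 and 46% at 0.70, so the figure reproduces at the top of the range only. The source data were before-and-after measurements in one group. Read as a paired test, n=15 gives 97% and 71%. The power figures below use the two-sample reading.

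**Bias.** Let the placebo responses be pD and pM, the true effects tD and tM, and D = pD - pM. With 8:8 sham, the pooled sham mean is (pD + pM)/2.

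- DPFC vs pooled sham: (tD + pD) - (pD + pM)/2 = tD + D/2
- MC vs pooled sham: (tM + pM) - (pD + pM)/2 = tM - D/2
- DPFC vs MC: (tD - tM) + D, whether taken directly or as the difference of the two lines above
- All real (32) vs all sham (16): (tD + tM)/2 + (pD + pM)/2 - (pD + pM)/2 = (tD + tM)/2, so D cancels

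Simulation with D = 0.5 and no true effect gave +0.250, -0.250, +0.500 and 0.000.

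**False-positive rate, no true effect, nominal 5%** (simulation for the first column, where sham is a mixture of two means; noncentral t for the second):

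| D (SD) | DPFC vs pooled sham | DPFC vs MC |
|---|---|---|
| 0.2 | 5.8% | 8.5% |
| 0.3 | 6.8% | 13.0% |
| 0.5 | about 10% | 27.8% |
| 0.8 | about 17% | 59.1% |

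With the same true effect of 0.70 at both sites and D = 0.3, power is 64% for DPFC and 32% for MC, against 48% for each at D = 0.

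**Cost of matching** (SE in SD units):

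| Contrast | SE | Power at 0.70 | Power at 1.08 |
|---|---|---|---|
| Real vs pooled sham, 16 v 16 | sqrt(1/16 + 1/16) = 0.354 | 48% | 84% |
| Real vs same-site sham, 16 v 8 | sqrt(1/16 + 1/8) = 0.433 | 34% | 66% |
| DPFC vs MC direct, 16 v 16 | 0.354 | 48% | 84% |
| (real - sham at DPFC) - (real - sham at MC) | sqrt(2/16 + 2/8) = 0.612 | 20% | 41% |

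The ratios are 0.433/0.354 = 1.22 and 0.612/0.354 = 1.73.

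**Bias against variance.** RMSE of a pooled per-site effect is sqrt(0.125 + D²/4). It equals the matched 0.433 when D²/4 = 0.0625, so D = 0.5. RMSE of the direct site contrast is sqrt(0.125 + D²). It equals 0.612 when D² = 0.25, again D = 0.5. Below 0.5 SD the pooled and direct estimates have the smaller RMSE.

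**Overall contrast with site as a factor.** Without site: sqrt(1/32 + 1/16) = 0.306. Averaging the two within-site contrasts: sqrt(0.25 × 2 × (1/16 + 1/8)) = 0.306. Under 2:1 allocation at each site, nothing is lost.

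**The case against.** Nothing in the documents shows that D differs from zero. The electrodes are in the same place for every session, which may make the two shams feel alike, and the primary measure is pressure QST on the forearm, where no site-dependent placebo response is suggested. The plan never says that the two shams are pooled for the per-site effects. It only leaves sham unqualified, and one sentence under MRI scanning pairs active and sham with each strategy, which could hint at matching. Pooling is also a reasonable trade in a small pilot: it has the smaller RMSE while D is below 0.5 SD. Finally, the sham difference itself rests on 8 v 8. Its 95% half-width is about 2.0 to 2.1 × sqrt(2/8), or about 1 SD, so it could not show whether D is present or absent.

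Most of this stands. It rules out replacing the pooled estimates and limits what the matched ones can show. It does not remove the point: the sentence under MRI scanning defines no model, the stated grouping has no sham-site term, and the planned site comparison cannot separate a treatment difference from a placebo difference.

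A reader might also infer that the main analysis is biased. The documents do not support that. Taken literally, the Outcome Measure(s) grouping has two levels, and D cancels there.

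**Conclusion.** The point holds for the per-site effects and the comparison of the two sites, and only if D is not zero. The shift is +D/2, -D/2 and D. At an assumed 0.2 to 0.8 SD, that is 0.1 to 0.4 SD in size for each site effect and 0.2 to 0.8 SD in the site comparison. For a site against sham, the error inflation is small at the low end of that range. The site comparison is the more exposed result.

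The result rests on sham staying 8:8. Unequal dropout by sham site changes each site's share, though the site comparison still carries all of D. It would also bias the overall contrast, by D times the difference between the DPFC shares of the real and sham groups.

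Two stronger readings are tempting. One is that the pooled effects are known to be wrong. The documents give no D, so this is unsupported. The other is that matched contrasts should replace the pooled ones. Below 0.5 SD that would make the estimates less accurate overall.

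**What to change.** 1. Name the comparator. Keep the pooled-sham effect for each site and the direct DPFC-MC contrast, and say that sham there means both sites together.
2. Put stimulation site, for real and sham participants alike, into the overall real-vs-sham model. This costs no precision under the planned allocation and protects against unequal dropout by sham site.
3. As sensitivity analyses with confidence intervals, report real vs site-matched sham for each Aim, and (real DPFC - sham DPFC) - (real MC - sham MC).
4. Do this for MRI only as far as cell sizes allow, since some participants will not be scanned and some scans will be lost to motion.
5. Do not present the direct or pooled site comparison as free of site-specific placebo effects.
6. State in Sample Size that the matched control has 8 participants per site, with the lower power shown above, and that the sham DPFC-minus-MC difference is too imprecise (95% half-width about 1 SD) to show that D is absent.

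The cost is analysis wording and one factor in the models, with no new participants or data. The sensitivity results will have wide intervals, with the 22% and 73% larger standard errors stated beside them.

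### The plan lets an unstated number of participants skip MRI and says integrity is unaffected; that holds for the sensory-testing sample, but scanned arms can fall below the n=15 behind the only power figure.

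*Combined protocol and SAP*

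**What the plan says.** All places are in the combined protocol and SAP.

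- **Sample Size, basis.** "A power estimate for Aim 1 and 2 was prepared using an original fMRI dataset previously collected in our laboratory". The source is 18 healthy controls scanned before and after one session. The effect sizes run from 0.70 (thalamus) to 1.08 (insula), and the section concludes "n=15 yields 80% power using a two-sided p<0.05". It names no test and does not say whether 15 is per arm.
- **Sample Size, losses.** "Allowing for a 10% dropout rate after the screening visit, and up to a 20% dropout rate" by the end of treatment, and "a 10% data loss rate for MRI (Aim 2) due to individuals with excessive head motion in the MRI scanner". Screening 58 is said to give 48 with complete data, 16 per arm.
- **Sample Size, COVID paragraph.** "some participants will not receive the MRI" portion, because of scheduling and reluctance to wear a mask in the scanner. Then: "This will not affect our total enrollment goals, nor compromise the scientific integrity of this study". There is no expected number, cap, minimum scanned per arm or revised power.
- **Sample Size, allocation.** A Latin square is meant to keep enrolment even across groups. MRI participation is not a stratum.
- **Status of the outcomes.** The Exploratory Aim under Objectives and the Exploratory Analysis paragraph both contain the words "While the primary outcomes will be MRI V1 vs V2". The Assessments paragraph instead calls the QST thresholds primary.

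**The concern.** An unchanged enrolment total does not protect an outcome that only scanned participants can supply. A participant who skips MRI fills one of the 48 places and contributes nothing to the first-versus-second scan comparison. If the plan's 16 completers per arm are taken at face value, there is one spare scan per arm (16 − 15), or 3 of 48, before an arm falls below 15.

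The plan also does not say when MRI status is settled. Randomisation follows the Screening visit, and the MRI visits follow enrolment, so the text permits a decision to skip after the arm is set. For the second and third scans it could come after experience of the sessions. The scanned subset would then no longer be a fully randomised comparison.

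At stake is the reliability of the imaging effect sizes that this pilot is meant to pass to a larger trial.

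**Working it through.** **Inputs.** From Sample Size: two-sided alpha 0.05; effect size d = 0.70 to 1.08; n = 15 for 80%; 16 per arm; 58 screened; losses of 10%, 20% and 10%. The skip rate is not given, so 10%, 25% and 50% are assumptions.

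**Formulas.** Noncentral t power. Two-sample with n per arm: df = 2n − 2, noncentrality d√(n/2). Paired within arm: df = n − 1, noncentrality d√n.

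**Step 1: reproduce n = 15.**
- Two-sample, d = 1.08: 81.5% at 15 and 78.5% at 14, so 15 is the smallest n reaching 80%.
- Two-sample, d = 0.70: 34 per arm needed; 15 gives 45.7%.
- Paired, d = 1.08: 9 needed. Paired, d = 0.70: 19 needed; 15 gives 71.3%.

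Of the two quoted effect sizes, only 1.08 with a two-sample test yields 15. A paired test gives 80% at 15 if d is about 0.78, which lies inside the range but is not quoted.

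**Step 2: power by number scanned per arm**, starting from 16 completers and before motion loss.

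| Skip rate (assumed) | Scanned per arm | Two-sample 1.08 | Two-sample 0.70 | Paired 1.08 | Paired 0.70 |
|---|---|---|---|---|---|
| 0% | 16 | 84.0% | 48.3% | 98.1% | 74.5% |
| 6.25% (3 of 48) | 15 | 81.5% | 45.7% | 97.3% | 71.3% |
| 10% | 14.4 | 79.8% | 44.1% | 96.6% | 69.2% |
| 25% (12 of 48) | 12 | 71.5% | 37.5% | 92.5% | 59.9% |
| 50% (24 of 48) | 8 | 52.0% | 25.7% | 74.6% | 40.1% |

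**Step 3: the plan's own losses, with nobody skipping.** 58 × 0.9 × 0.8 × 0.9 = 37.6 usable scans; 37.6 / 3 = 12.5 per arm. At 12.5, two-sample power is 73% at d = 1.08 and 39% at d = 0.70. If 25% then skip, 12.5 × 0.75 = 9.4 per arm, giving 60% and 30%.

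**Step 4: unevenness.** If 36 of 48 are scanned, with skipping unrelated to arm, the largest and smallest arms differ by 4 or more with probability 0.32 (simulation); with 24 scanned it is about 0.42. The cost is small: at d = 1.08, 12 versus 12 gives 71.5% and 10 versus 14 gives 70.3%.

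**The case against.** The strongest reply is that QST is the primary measure. The Assessments paragraph says so, and the words that make MRI primary sit inside exploratory paragraphs, where they may only contrast the early scan comparison with later durability. Skipping MRI removes nobody from the QST or questionnaire sample, and Outcome Measure(s) describes a pilot meant to develop effect sizes. This stands for QST. It does not cover the imaging aims: Hypothesis 1 of both Aims concerns the brain's response to pain, the only power figure is an imaging one, and the assurance is not limited to any outcome.

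Three stronger readings may tempt a reader.

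- **That losing more than one scan per arm always takes power below 80%.** This is true of the two-sample reading at 1.08. On a paired reading at 1.08, power is still 92.5% at 12 and 80.9% at 9. The plan names no test, so the flat statement is not supported.
- **That the scanned arms will be badly depleted.** The plan says only that some will skip. At 10% skipping, two-sample power at 1.08 is 79.8%, almost the stated 80%. If exactly 3 of 48 skip, a gap of 4 between arms is impossible.
- **That the imaging comparison is biased.** The reasons given are scheduling and masks, not arm. Design puts the first scan before the first stimulation visit, and the sham is active with checks on blinding. Skipping after experience of the sessions is possible for later scans, but nothing shows that it is expected.

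It can also be said that the Latin square is described as working with replacement, so unscanned participants might be replaced. The text ties that to even enrolment across groups, not to scans, and the enrolment goal is left unchanged.

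**Conclusion.** The assurance is supportable for QST and questionnaires and unsupported for imaging. The number who skip is open, nothing sets a minimum scanned per arm, and allocation takes no account of MRI status, so the scanned arms can become small. Small arms, not unequal ones, cause most of the lost power.

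The size depends on two things the plan leaves out: the test and the skip rate. With a two-sample test at 1.08, power runs from 79.8% (10% skipping) through 71.5% (25%) to 52% (50%). At 0.70 it is already 46% at 15 and 37.5% at 12. A paired test is far more forgiving at 1.08, but at 0.70 gives 71% at 15.

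A reader might blame the whole shortfall on COVID skipping. The documents do not support that: the plan's own dropout and motion rates already leave about 12.5 usable scans per arm, and skipping adds to a gap that exists without it.

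All these percentages take the planning effect sizes as given. Those come from a heat-pain task, whereas the MRI scanning paragraph lists only an anatomical and a resting-state scan, so they may not describe the contrast actually analysed.

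**What to change.** In Sample Size:

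1. Limit the integrity sentence to the QST and questionnaire outcomes.
2. Name the test behind n = 15 and say whether 15 is per arm.
3. State imaging power, or confidence-interval width, across 0.70 to 1.08 at the expected number of usable scans per arm after dropout, motion loss and skipping.

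In Sample Size and the rTMS Treatment sessions paragraph:

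4. Record MRI yes or no before allocation, and allocate 1:1:1 within each status.
5. Define the imaging analysis set as everyone allocated as an MRI participant, and report how many of them lack a usable pair of scans.

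In the Analytical Plan:

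6. Tabulate baseline pain and opioid use for scanned and unscanned participants.

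**Cost.** One earlier question, a second allocation list, a few more incomplete blocks (noticeable at 48 participants, with sham also split by site) and a stated imaging power that will probably be lower than 80%. Stratifying keeps the imaging comparison randomised and balanced. It does not recover lost scans.
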